3. DATA COLLECTION

3.1 KEY OUTCOMES

This section describes the key outcomes and unit of analysis. Each research question focuses on different indicators based on the data collected. The pre-analysis plan in Appendix 1 describes the analytic model and metrics for each research question in more detail. Some indicators for the process evaluations will be based on data collected during nudge installation. The remaining indicators will be based on observed data collected during the end-line.

The primary research question (RQ1) will specifically target two groups of pupils at sample schools: pupils from grade 1-3, and pupils from grade 4-6. UNICEF and DepEd are interested in the potentially different impact of the intervention on pupil iHWWS in both of these grade groups, in order to inform in which grades to implement the nudges in the future. The impact may differ between these two groups due to different receptiveness to motivators for handwashing behavior targeted by the nudges, or different pre-existing pupil behaviors and perceptions around handwashing. The two age groups were identified in collaboration with UNICEF and are in line with the distinction often made in schools between "lower grades" (1-3) and "higher grades" (4-6). We will report estimates for the pooled sample, but will also conduct sub-group analysis to determine whether the impact of the key outcomes for this research question was statistically significantly different in the two samples.

In addition, within each sample, sub-group analysis will be conducted to compare the average impact of the behavioral nudges by:

- pupil gender
- enumerator gender
- WinS implementation quality index score
- whether the handwashing environment is conducive to nudges, as determined by a constructed index on homogeneity of the toilet and handwashing environment (see Table)
- class size

More information on the analytic models used for each research question, sub-group analysis and covariates included is provided in the pre-analysis plan in Section 6. An overview of the key indicators, unit and sample for each research question is presented in Table 1 below.

Table 1: Key Outcomes by Research Question

RQ.	Outcome category	Outcome	Unit (sample)
RQ1 Independent (impact) handwashing after toilet use		Pupil washed hands with soap and water after toilet use	Pupil (grade 1-3 & grade 4-6)
		Pupil washed hands with water after toilet use	Pupil (grade 1-3 & grade 4-6)
RQ2	(a) Availability of handwashing facilities with	Availability of functioning handwashing facilities	School
(impact)		Availability of functioning handwashing facilities with soap	
	water and soap	Presence of functional handwashing facility with soap near toilet facility	Toilet facility
		Presence of functional handwashing facility near toilet facility	
RQ3 (process	Implementation of nudges	Presence of nudges at intended location in handwashing facility or toilet facility	Toilet facility
)		Condition of nudges at handwashing facility or toilet facility	

Pre-analysis plan [DRAFT] | January 20, 2020

3.2 DATA COLLECTION ACTIVITIES

Table 2 outlines our plans for data collection activities and timing. We plan to observe handwashing behavior 3-4 months after implementation to measure the medium-term effects. Drawing on our experience assessing HiFive³¹ in 2017 and 2018, we will measure handwashing through in-person observations by trained enumerators. Structured observation is regarded to be among the most reliable methods of measurement in many contexts.³² Enumerators will visit all schools in the sample, and record observations using SurveyCTO. To minimize observer effects, they will inform principals, teachers, and students only that they are observing general classroom activities. We will detail additional procedures for enumerators during training and in our Data Collection Guidelines document, to be created prior to the endline observations.

Data Collection tools for immediately after implementation and 4 months post-implementation will be developed in the coming months. We will pilot these tools at a subset of schools that were excluded from our sample because they will be receiving additional WASH programming from another DepEd partner during the duration of our study. These schools also hosted piloting of our nudge installation protocols, and will therefore be appropriate for testing the portion of our data collection tools related to nudge implementation (RQ3).

IDinsight will ensure data quality by following robust protocols, including:

- Enumerator training to ensure enumerators make classroom observations correctly and consistently
- Spot-checks on enumerator by IDinsight staff to ensure correct and consistent procedure and data entry
- Frequent data back-checks by IDinsight to spot and correct any data collection flaws in real time
- Use of Survey CTO software for data collection through all survey instruments, as SurveyCTO's internal checks and clear interface reduce risk of enumerator error
- Application of various quality control checks during initial data analysis, including checks for missing data and data entry checks

³¹ Please see Footnote 2 for more information about the HiFive intervention and HiFive Phase I and Phase II evaluation.

³² Please see Section 1.3 Evidence Review.

Table 2: Overview of Data Collection Activities

Assessment Component	Data Collection Activities	Time relative to implementation	Description
1. iHWWS rates (impact evaluation, RQ1)	iHHWS after toilet use observations in classroom (treatment & control)	4 months post- implementation	Enumerators will observe whether pupils wash their hands with soap, wash without soap, or do not wash, after they have used classroom toilets. This will be used to estimate the causal impact of the nudges intervention on iHHWS rates.
2. Homogeneity in toilet and handwashing environment (impact evaluation, RQ1)	Structured facilities observations for both treatment and control (treatment & control)	4 months post- implementation	Structured observations of each facility will assess factors such as: presence of existing WASH-related informational posters, whether the handwashing area is used for other non-WASH purposes (e.g. storage, dish-washing area), whether the handwashing station has objects unrelated to handwashing ³³ , how many primary colors are present in health corner where handwashing station is present, and other factors related to visual clutter to be finetuned after piloting. These will be used to construct a measure of whether the facility is conducive to nudges, to be used in subgroup analyses.
2. Access to soap and water (impact evaluation, RQ2)	Structured facilities observations (Treatment & control)	4 months post- implementation	Structured observations of whether classroom handwashing facilities including soap and water. These will be used to estimate the causal impact of the nudges intervention on pupil access to soap.
3. Nudges implementation (process evaluation, RQ3)	Structured facilities observations (treatment)	During implementation visit but after nudge installations are completed	Structured observations of facility after implementation, to assess presence and condition of nudges in toilet and/or handwashing station. These will be used to assess if installation proceeded as intended.
4. Nudges implementation (process evaluation, RQ3)	Structured facilities observations (treatment)	4 months post- implementation	Structured observations of presence and condition of nudges in toilets and/or handwashing facilities. These will be used to assess if installed nudges functioned and lasted as expected.

³³ A concern is that handwashing areas both across and within schools may differ in terms of how conducive they are to nudges; more cluttered and busy environments may dilute the impact of nudges.

Pre-analysis plan [DRAFT] | January 20, 2020

4. TECHNICAL RISKS AND MITIGATION STRATEGIES

"Clutteredness" in school handwashing environment

Schools in our sample may differ in terms of baseline toilet and handwashing facility environments. A potential concern is that among handwashing areas that are cluttered and busy, all nudges by the handwashing area (footpath, arrow sticker, eye sticker) would be less likely to grab attention by producing the necessary element of surprise; therefore, any potential impact of the intervention may be diluted. This is particularly likely if the bathrooms already have existing WASH-related informational posters, are crowded with other features (e.g. cabinets or items for storage), or used for other purposes such as tooth-brushing or cleaning dishes. Since we hypothesize that baseline bathroom "clutteredness" factors like these mediate the impact of nudges, substantial differences in the toilet/handwashing environment present the risk of reducing the impact of nudges overall. If the average school is very cluttered, we may not have a large enough sample size to estimate the differential effects of the nudges in cluttered schools and uncluttered schools.

We address this risk in two ways:

1) During school sampling, we prioritized selecting schools with "nudge enabling" handwashing environments, based on characteristics available in the OMS data which we hypothesized could reflect conduciveness to nudges. This is described in Section 2.5 Recruitment of Participants (Sampling).

2) Given that OMS data is at the school-level and there may be difference within a school in terms of handwashing facilities, during our endline data collection, we will also collect detailed information on toilet and handwashing facility environment. Using this data, we will explicitly model for heterogeneity of "nudge enabling" environments in our analysis of the impact of nudges.

Observer effects and social desirability bias

Measuring handwashing behavior is challenging, since it is particularly prone to over-reporting and difficult to observe directly, as described in Section 1.3 Evidence Review. Based on this review, this evaluation will use a combination of indicators that are cost- and time-effective, and meet the practical needs and constraints for the evaluation, in order to measure handwashing practices among pupils. The research team carefully designed and piloted the observation protocols to minimize influence of observation on handwashing behavior, and to mitigate potential reporting biases. These protocols have also been successfully refined and used in two previous IDinsight studies to observe handwashing in DepEd schools in the Philippines.

For indicators based on observed data, the risk of observer effects will be mitigated by not revealing to teachers and pupils in observed classes the specific information that the observer will collect throughout the observation period. While DepEd will be informed about the overall aim of the study, and permission will be obtained from teachers for observing their class, enumerates will state to teachers that the reason for observation is to observe "normal classroom activities," with no mention of handwashing, sanitation, or WinS programming. Further, it is important to note that if there is any behavior change as a result of observation despite the precautions put in place to minimize this, given the nature of random assignment, it is assumed that any resulting change in behavior would, on average, be similar across the treatment and control schools. Therefore, the impact estimate will still provide an unbiased estimate of the impact of the behavioral nudges. These measures are intended to mitigate biases in data collected on handwashing behavior.

Treatment compliance

Within our study, treatment-compliant schools refer to schools assigned to treatment that receive the nudges and maintain them over the course of the intervention, and schools assigned to control that do not implement the nudges. This intervention does not require schools or principles to take any action other than providing nudge installation teams permission to visit and implement the nudges, which are presented to them as desirable classroom improvements. Therefore, non-compliance among treatment schools is not likely. While it is possible that teachers may remove nudges after implementation, we conducted focus groups with teachers during the intervention design phase to ensure teachers did not have strong objections to the presence of the intervention nudges in their classrooms. We will also conduct orientation with all treatment school principals to receive their support for nudge installation.

Non-compliance among control schools is also unlikely. While it is possible that there may be replication of the nudges in control schools, which are cheap and scalable environmental changes that are easily replicable, we will minimize this risk through our implementation protocols. We will limit communication about the nudge installations, and the exact specification of the nudges, to relevant individuals to treatment schools, primarily principals. We will also ensure DepEd does not announce the nudge installation plans to control schools.

As such, our estimates will be intent-to-treat (ITT) estimates. Nonetheless, we will also record at endline whether any treatment schools removed nudges or any control schools introduced nudges. In the event we find non-compliance, we will also estimate treatment-on-the-treated effects.

Spillovers

Potential spill-overs are expected to be minor, and would likely result in the treatment estimate being a lower bound of the impact of the program. The nudges intervention was randomly assigned at the school-level. Distances between schools within Zamboanga del Norte vary. Spillovers would occur when students from schools of different treatment statuses interact. For example, students from treatment schools who interact often with friends and family from control schools with lower handwashing rates may be influenced to was their hands less often than treatment students without such friends. Students may also transfer between schools of different assignment statuses during the study, such that a student from a treatment school may transfer into a control school and influence their new classmates to wash their hands more often. However, pupils are expected to attend schools closest to their homes, and to have friends who are also from their *barangay* (neighborhood) and who would attend the same school. Therefore, spillovers are unlikely to have a meaningful effect on the treatment estimates.

Representativeness and External Validity

We intend to generate evidence on the effectiveness of behavioral nudges to inform national scaleup plans in the Philippines, and to add to the global body of research on handwashing and behavioral change interventions.

The target population for the nudges intervention includes pupils in grades 1 to 6 in selected elementary schools in Zamboanga del Norte. It is important to note two ways in which these schools may differ from other schools in the Philippines. First, these schools are located in DepEd school divisions in which UNICEF has designated a priority target district for WinS programming. These areas are chosen because of high rates of poverty as well as particularly willing partners in the associated DepEd Division offices. Second, schools that were identified as eligible for the intervention, and were included in the evaluation sample, met minimum inclusion criteria related to the current WASH conditions and programs being implemented at these schools, as described in Section 2.5 Recruitment

Pre-analysis plan [DRAFT] | January 20, 2020

of Participants (Sampling). It is important to keep in mind the characteristics of the schools participating, when considering how the evaluation findings may predict the impact of the intervention in other schools in the Philippines. However, it is also important to note that the intervention is intended for, and meant to be scaled up in, environments similar to those meeting our minimum inclusion criterial; that is, classrooms with minimum handwashing enablers such as facilities, water, and soap.

For outcomes based on pupil classroom observations, all grade 1-6 pupils at sample schools will be eligible for the evaluation sample frame, with the exception of pupils in classrooms where the only handwashing facility available to pupils when in class is not observable (only inside the toilet and not visible to surveyors), or there is no toilet for pupils to use inside or directly outside the classroom.

DIDINSIGHT DATA. DECISIONS. DEVELOPMENT.

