1.2 INTERVENTION

1.2.1. INTERVENTION OVERVIEW

The intervention will install behavioral "nudges" in the handwashing environment to influence pupils' handwashing behavior. The nudges are designed to address the primary barriers to handwashing

¹ The program was designed as part of a partnership between DepEd, LGUs, GIZ and GlaxoSmithKline.

² We previously conducted the HiFive for Hygiene and Sanitation ("HiFive") Phase I and Phase II evaluations. HiFive was a behavior-change intervention that focuses on motivating improved independent handwashing behavior and triggering discussions on how to better maintain clean and functional handwashing facilities. Phase I was an impact evaluation to estimate the causal effect of the intervention on iHWWS rates among elementary school children in the Philippines. Phase II was a process evaluation to assess the program's implementation. HiFive as a handwashing intervention was a precursor to the nudges intervention, and our experience with HiFive prompted the development of the nudges study and evaluation.

among children in the Philippines, which our previous studies have found to be forgetfulness and more broadly, a lack of habit formation.³

There are two intervention points:

- 1. Reminders to children to wash their hands immediately after they use the toilet. This counteracts forgetfulness and present-bias.
- 2. Relatively low-cost changes to the physical environment to provide subconscious cues that encourage children to approach the handwashing station. This increases the salience of handwashing and therefore make the behavior more likely.

Based on smaller-scale prior studies⁴⁵, we have identified several promising nudges. These were chosen and adapted to be culturally appropriate, contextually feasible, cost-effective, and scalable for implementation sites in the Philippines:

- 1. Visible signage crafted to trigger behavioral motivators for handwashing
- 2. *Colorful pathway* overlaid with footprints leading from the toilet to the handwashing station
- 3. Sticker of a pair of eyes placed above the handwashing station
- 4. *Soap dish with an arrow* beside it on the sink or counter to remind children to wash their hands with soap

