5. ETHICAL CONSIDERATIONS

ETHICAL CLEARANCE

Given the nature of the evaluation activities and the relatively low sensitivity of the survey questions, the study poses little risk to participants. IDinsight will apply for ethical clearance for the research through a research ethics committee accredited by the Philippine Health Research Ethics Board (PHREB). We will apply for ethical clearance for the study in October 2019, after we have finalized the evaluation design and prepared all the necessary documentation.

RECRUITMENT STRATEGY

DepEd national and division staff were consulted in the design of the nudges and evaluation. DepEd divisions and treatment schools in Zamboanga del Norte will be provided information of the details of the nudges and installation prior to implementation. This will be done either in-person or via phone by either IDinsight staff or supporting members of DepEd.

No additional implementation activities will be conducted and no supplies will be distributed to schools or pupils as part of the evaluation. In addition, WinS programs have previously been implemented in these school divisions with support from UNICEF, and all participating schools (both treatment and control) may thus be familiar with both WinS programs and UNICEF.

INFORMED CONSENT & ASSENT

Prior to visiting schools, letters from DepEd divisions will be obtained, and will be presented to principals at all schools visited to describe the research aims and activities, and confirm DepEd authorization. Upon first arrival at each school, permission will be obtained from the principal prior to collecting any observation or survey data.

Once principal permission is granted, teachers of classes selected for observation or pupil surveys will be sensitized about the study and the data collection activities.

CONFIDENTIALITY

All pupil observations will be conducted at the school. The observations will be conducted inside the pupils' classroom or at the group handwashing station, and we will not collect uniquely identifiable information about pupils.

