³⁴ The approach to test the difference in impact of the program for these two sub-samples will be separate regressions for each sub-sample and then a test comparing the treatment effects across the two regressions. This will be performed instead of a single regression on the pooled sample with an interaction term between the treatment term and the sub-sample for the sake of simplicity, as the former approach would require multiple interaction terms for all co-variates, as well as threeway interactions when exploring other sub-groups.

Note on sample weights: Sample weights will be included to account for the fact that the sampling probability of classes for a given grade is different across schools. Since a constant number of classes will be sampled for each grade in each school³⁵, schools with more classes for a given grade will have a lower probability of being selected. This will be accounted for by using weights that represent the inverse probability of class selection. By doing so, each pupil observed or surveyed will have the same probability of inclusion into the sample.

Table 3 below provides a summary of the indicators for this research question, and the unit of analysis and sample corresponding to each indicator. Table lists the co-variates we will use in addition to the indicators in our analytical models to answer research question 1. We will report estimates for our outcome indicators both with and without controls.

³⁵ For classroom observations, one class in each grade in each school will be sampled independent of the total number of classes in the grade.

Pre-analysis plan [DRAFT] | January 20, 2020

Outcome category	Outcome	Metric	Unit	Sample	Analytic model ³⁶ (LPM – linear probability model ; OLS – ordinary least squares)
Independen t	Pupil washed hands with soap and water after toilet use	Y.1 – binary variable for whether pupil was observed to wash hands with water and soap after toilet use	Pupil	Separately for: Grade 1-3 pupils Grade 4-6 pupils	LPM: Y = Y.1
handwashin g after toilet use	Pupil washed hands with water after toilet use	Y.1 – binary variable for whether pupil was observed to wash hands with water after toilet use at school	Pupil	Separately for: Grade 1-3 pupils Grade 4-6 pupils	LPM: Y = Y.1

Table 3: Outcome Indicators for Research Question 1

³⁶ Unless otherwise stated, the independent variable of interest is treatment assignment.

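### The RQ1 sample frame keeps classrooms with both a visible and an in-toilet handwashing station, so detection of the primary outcome may differ by arm, in a direction and amount the plan does not fix

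*SAP*

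**What the plan says.** - **Sample frame** (Section 4, Representativeness and External Validity). All grade 1-6 pupils at sample schools are eligible, "with the exception of pupils in classrooms where the only handwashing facility available to pupils when in class is not observable". The parenthesis that follows explains this as "only inside the toilet and not visible to surveyors". The only other exclusion is a class with no toilet inside or directly outside the room.
- **Outcome** (Section 6, Table 3). Both RQ1 outcomes, soap with water and water, are a "binary variable for whether pupil was observed to wash hands" in the stated way after toilet use.
- **Recording** (Section 3.2, Table 2). "Enumerators will observe whether pupils wash their hands with soap, wash without soap, or do not wash, after they have used classroom toilets". These are the only three categories.
- **Observer position** (Section 5, Confidentiality). "The observations will be conducted inside the pupils' classroom or at the group handwashing station".
- **Intervention** (Section 1.2.1). One nudge is a coloured pathway "overlaid with footprints leading from the toilet to the handwashing station". The physical changes are described as "subconscious cues that encourage children to approach the handwashing station".
- **Argument for an unbiased estimate** (Section 4, Observer effects and social desirability bias). If pupils react to the observer, "it is assumed that any resulting change in behavior would, on average, be similar across the treatment and control schools".

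**The concern.** The exclusion shows that the authors knew in-toilet stations defeat measurement, but it removes a class only when the hidden station is the sole one. In a class with both kinds, a pupil may wash unseen.

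If that happened equally often in both arms, it would lower both observed rates and mainly cost sensitivity. It need not be equal here, because the intervention acts on the route from the toilet to the station. A treated pupil who would have washed inside the toilet may wash at the visible station instead. The observed rate then rises although no more handwashing took place. This arises after assignment and through the treatment, so randomisation does not remove it.

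The observer-effects argument concerns pupils who behave differently because they are watched. It says nothing about washing that the observer cannot see. At stake is the primary endpoint, and with it the scale-up decision that Section 2.5 ties to it.

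**Working it through.** **1. The plan's own design figure.** Inputs from Section 2.5: 10% against 17%, alpha 0.05 (taken as two-sided), power 0.8, ICC 0.1, 26 observations per school, 100 schools.
- Pupils per arm without clustering: 373.
- Design effect: 1 + (26 - 1) x 0.1 = 3.5.
- Schools per arm: 373 x 3.5 / 26 = 50.2, against 50 stated. Power at 50 per arm is 0.798.

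The design figure reproduces, so 7 points is a fair yardstick.

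**2. Does the text handle an unseen wash?** Table 2 has no such category. The missing-value rule in Section 6 (Outliers and Missing Values) gives a replacement only for covariates. No covariate in Table 4 identifies a hidden station; X.6 describes nudge conduciveness. The document has neither an exclusion nor a sensitivity analysis for mixed classes.

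**3. Form of the bias.** Let h be the share of observations in mixed classes, r the rate of washing at the hidden sink without nudges, d the share of that washing moved to the visible station, and u any new hidden washing caused by nudges. Hidden washing under treatment is r(1 - d) + u. If unseen washes are recorded as no wash:

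observed effect = true effect + h x (r x d - u)

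The added term is positive when r x d exceeds u and negative when u exceeds r x d.

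**4. Size with u = 0.** The SAP gives none of h, r and d. Assumed: h from 0.1 to 0.4 and d from 0.3 to 0.8. For r, two anchors from Section 2.5: about 2% (rate in the previous study) and 10% (planning rate for controls, which the SAP calls an overestimate).

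| r | low (h 0.1, d 0.3) | middle (h 0.3, d 0.5) | high (h 0.4, d 0.8) |
|---|---|---|---|
| 2% | 0.06 points | 0.3 points | 0.64 points |
| 10% | 0.3 points | 1.5 points | 3.2 points |

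The middle case is 0.3 / 7 = 4% of the minimum detectable effect at r = 2%, and 1.5 / 7 = 21% at r = 10%.

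**5. Effect on the test.** Suppose true washing is 10% in both arms, half the pupils are in mixed classes, half of their washing is hidden in controls, and all of it moves under treatment. The artefact is 0.5 x 0.10 x 0.5 x 1 = 2.5 points (7.5% against 10% observed). It would be declared a significant benefit with probability about 0.23 at 50 schools per arm and 0.28 at 66, against a nominal 0.025 in that direction. With only 10% of pupils in mixed classes and the other inputs unchanged, the artefact is 0.1 x 0.10 x 0.5 x 1 = 0.5 points and the probability at most about 0.045.

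**6. Water outcome.** Washing with soap and water is a subset of washing with water, so r cannot be smaller for the water outcome. With the same h and d, neither can the relocation term.

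**The case against.** - **No coding rule is written.** A reader might infer that the plan scores unseen washes as not washed. It does not say so. That is the natural consequence of Tables 2 and 3, but Section 3.2 leaves further enumerator procedures to Data Collection Guidelines and tools still to be developed. This stands, and the point is worded accordingly.
- **The documents do not show that mixed classes exist.** Section 2.3 says most schools have a toilet and handwashing facilities in each classroom, not two stations per class, and Section 2.6 requires only one station per school. This stands: h could be close to zero.
- **The sign is open.** A reader might infer that the bias must favour the intervention. That needs nudges at the visible station only. The SAP does not say which station is nudged where there are two. Section 1.2.2 describes bathroom signs as reminders, and Table 2 checks nudges in toilets and/or handwashing stations. Such nudges could raise unseen washing in treated schools and hide a real benefit. This stands.
- **The larger sizes rest on a high rate.** A reader might quote a bias of about one fifth of the target effect. That puts a 10% soap-washing rate at the hidden sink alone. At the documented rate of about 2% the same inputs give 4%. This stands, with one reservation: earlier observed rates may also have missed hidden washing, so 2% is not a ceiling.

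None of this closes the gap in the frame, which is a rule stated in this document and not a detail left to a manual.

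**Conclusion.** The concern holds in limited form. The frame admits classes in which part of the outcome cannot be seen, the outcome is defined by what was seen, and the intervention can change where pupils wash. Detection of both RQ1 outcomes may therefore differ by arm, and nothing in the SAP prevents, measures or tests this.

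Neither sign nor size is established. If only the visible station is nudged, the bias favours the intervention by 0.06 to 0.64 points at a hidden-sink soap-washing rate of 2%, or 0.3 to 3.2 points at 10%, against 7 points. These figures rest on assumed values of h and d and on unseen washes being recorded as no wash. The documents do not support a claim that the primary result will be spuriously positive. They support a claim that the plan could not tell if it were.

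**What to change.** 1. **Record it.** In the facility observation already planned for both arms (Table 2), note for each observed class whether pupils can use any handwashing station the enumerator cannot see. Define this by the fixed presence and position of the station, not by soap or water on the day, since RQ2 treats those as outcomes.
2. **Analyse it.** Estimate both RQ1 effects in classes where every usable station is visible, report this beside the estimate that includes mixed classes, and state before endline which is primary.
3. **Code it.** Add a value for events that could not be observed, so that they are not entered as no wash, and report its frequency by arm. State how these events enter the inclusive estimate. Simply dropping them would leave mainly visible washers in mixed classes, so showing both extremes (all washed, none washed) is safer.

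**Cost.** One form item, one response code and one added analysis. The restricted estimate loses some precision and applies to a narrower population.

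Excluding mixed classes before sampling is optional and dearer. It means screening every class before one is drawn per grade (Section 6, footnote 35), and where a grade has a single class it may remove that grade from the school and cut into the 26 observations planned.
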